We propose a proof of concept clinical trial to assess the validity of a novel foot offloading device (PopSole™) that allows for customized pocketing out of areas of pain, along with customized arch support and metatarsal height to optimize offloading.

An important part of recovery from foot injury (including fat injections, treatment of diabetic ulcers, wart removal, painful calluses, healing fractures) is the minimization of pressure to optimize healing. This offloading is challenging because current modalities limit patient function, work, and safety due to their bulk, weight, and attractiveness. (7) Aggressive modifications to shoe soles create asymmetry between the feet that can lead to gait instability, falls, and pelvic shifts. (8-15) We have another clinical trial to assess comparison of this device to our current standard of care method utilizing cutting metatarsal pads and adhering them to current insoles to reduce pressure on grafted areas, but this does not adequately reduce pressure on the fat grafted areas.

Our device can be used in conjunction with post-operative boots that have flat bottoms to augment them for more comfort and potentially enable earlier transition to regular shoe gear. It may be able to eliminate more bulky devices completely as PopSole™ can fit into a regular sneaker or dress shoe.

With our novel device PopSole™, we aim to expedite the recovery process, reduce pain, and reduce compensatory gait issues that could lead to falls. Patient balance and stability is a big concern with the presently available offloading modalities. Falls and injuries have been experienced by patients, especially elderly, neuropathic diabetic patients and physically challenged individuals. In addition, our device can be easily placed in a slide-on shoe for wear around the house, or in the shower.

Our primary aim of this validation project is to allow patients with foot pain to trial the device for 4 weeks to assess improvements in pain, assess fit and feel, durability, and compliance. This project will allow for modifications of the device to be made prior to future randomized studies to assess pressure and gait assessment, shear forces, and use in the diabetic population.

View: Pitt SF: Study Design

Study Design

1. Total number of subjects to be enrolled at this site (enter -1 for chart reviews, banking, registries):

20

2. Describe and explain the study design:

This is a prospective proof of concept study.

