Describe the primary and secondary study endpoints:

Primary Outcomes: Pain scores as assessed by validated outcomes measures, compliance over 4 weeks, durability of the device (do the bubbles hold up or require replacement).

Secondary Outcomes: Satisfaction with using the device, difficulties with the use of the device.

4. Provide a description of the following study timelines:

Duration of an individual subject's active participation:

Cohort 1: 4 Weeks

Cohort 2: 3 Months

Duration anticipated to enroll all subjects:

6 months

Estimated date for the investigator to complete this study (complete primary analyses):

6/30/2020

5. List the inclusion criteria:

Patients meeting the following criteria will be eligible to participate in the study:

- 1. Aged 18 years or older and able to provide informed consent
- 2. Subjects with foot pain due to forefoot or heel fat pad atrophy or chronic plantar fasciitis as defined by heel pain for greater than 6 months and failed non-surgical therapy
- 3. Willing and able to comply with follow up examinations

6. List the exclusion criteria:

Patients with the following characteristics will be excluded from participating in the study:

- 1. Concurrent injury to the lower extremity that would effect gait
- 2. Open foot ulcerations, fractures, or diagnosis of osteomyelitis of the feet
- 3. Surgical foot intervention in the last 6 months
- 4. Diagnosis of pregnancy or the intent of the participant to become pregnant during participation in this study
- 5. Neuropathy

- 6. Any issue that per the physician's determination would render the patient not appropriate to continue participation in the study (compliance, change in physical status, etc.)
- 7. Will children or any gender, racial or ethnic subgroups be explicitly excluded from participation?
 - Yes O No
 - * Identify the subgroups and provide a justification:

As foot pain due to forefoot or heel fat pad atrophy or chronic plantar fasciitis generally is not common in children, we will be limiting our population to adults 18 years of age or older.

8. Describe the power analysis used and cite your method of statistical analysis. If a power analysis is not possible, thoroughly justify the sample size required for the study, including appropriate literature citation (alternatively provide page reference in attached protocol):

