Pain and activity questionnaires will be performed at 3 time points during the trial. Repeated measures analysis of variance will be used to compare change over time in foot pain, and tissue thickness. A power analysis was performed based on preliminary data collected in our previously conducted clinical trial (PRO#016030521). To meet a power of 0.8 and alpha of 95% with effect size of 1.35, at least 10 human subjects will be needed to evaluate activities of daily living at pre and 4 weeks post-op.

View: Pitt SF: Research Activities

Research Activities

1. * Provide a detailed description of all research activities (including screening and follow-up procedures) that will be performed for the purpose of this research study. This description of activities should be complete and of sufficient detail to permit an assessment of associated risks.

All the following research activities are research procedures and are being completed for the purpose of this clinical trial. The following procedures will be completed prior to the PI's determination of subject's study eligibility. All screening procedures will take place at the Isaly's Medical building - UPMC Aesthetic Plastic Surgery Center and/or Lemieux Sports Medicine Complex. The information gathered during these visits will be from a combination of subject statement, medical record review, and in-person assessments and evaluations."

Optional digital recordings (i.e. photography) may be collected from any and all portions of the subject's research visits. These may include, but not be limited to, photos of functional assessment testing and clinical exams or photos of follow-up clinical course, etc. The study team will track/log those who agree to this vs. those who do not by including a section on the informed consent. This will also be kept in a spreadsheet to prevent us from taking photographs from subjects who have not authorized this activity. In addition, at follow-up visits, before any photographs are taken, participants will be asked again for verbal consent to the photographs.

COHORT 1:

Patients presenting with foot pain (pain in the forefoot, heel or plantar fascia) will be offered inclusion in the clinical trial. Information about the study will be provided at the time of candidate review. Once informed consent has been obtained then study procedures will be implemented for eligibility determination.

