 - * Describe the circumstances and any procedures for orderly termination: If the investigators feel that the subject cannot complete the study requirements safely (for example, experience severe side effects or development of an open ulceration), they may withdraw the subject from the study. At the time of withdrawal, the investigator will discuss with the subject the appropriate and requested follow up based on the specific event.
- Describe procedures that will be followed when subjects withdraw from the research, including partial withdrawal from procedures with continued data collection and data already collected:

Any identifiable research or medical information recorded for, or resulting from, participation in this research study including collected data and digital recordings, prior to the date that the subject formally withdrew their consent will continue to be used and disclosed by the investigators for the purposes described above and processed specifically as outlined in the research design for this trial.

Conflict of Interest

1	Answer YES if it is:
	 A study of a drug or device in humans to be submitted in a marketing application or reclassification petition that the applicant or FDA relies on to establish that the product is effective (including studies that show equivalence to an effective product); or
	 A study in which a single investigator makes a significant contribution to the demonstration of safety.
	Po NOT include:
	phase I tolerance studies or pharmacokinetic studies;
	 clinical pharmacology studies (unless they are critical to an efficacy determination);
	 large open safety studies conducted at multiple sites;
	■ treatment protocols; or
	 parallel track protocols. Does this study involve a Non-Significant Risk Device and you anticipate cluding the results as part of any type of submission to the FDA for approv
inc of (Does this study involve a Non-Significant Risk Device and you anticipate
ind of (Does this study involve a Non-Significant Risk Device and you anticipate cluding the results as part of any type of submission to the FDA for approvithis device? O Yes No s this study funded in part or whole by a PHS Agency? O Yes No

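### The plan does not specify outcome collection or analysis for participants whom investigators withdraw for harm or poor compliance, so results in those who remain could favour the device

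*Combined protocol and SAP*

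**What the plan says.** **Grounds for removal.** Risk and Benefits, item 7, answers yes to withdrawal without the participant's consent. Where investigators think someone cannot complete the study safely (the examples are serious side effects and a new open ulcer), "they may withdraw the subject from the study". Follow-up is then to be discussed with the participant according to the event. Separately, exclusion criterion 6 in Study Design covers any issue that, in the physician's view, "would render the patient not appropriate to continue participation in the study (compliance, change in physical status, etc".

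**Outcomes.** The endpoints entry in Study Design lists pain scores, compliance over 4 weeks and device durability as primary.

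**Data after withdrawal.** Risk and Benefits, item 8, asks about partial withdrawal with continued data collection as well as data already collected. The answer addresses only the second part: information recorded "prior to the date that the subject formally withdrew their consent will continue to be used". The visit schedules in Research Activities contain no early-withdrawal assessment.

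**Analysis.** Study Design, item 8, says: "Repeated measures analysis of variance will be used to compare change over time in foot pain". Questionnaires are taken at three time points. The item gives no analysis set, missing-data rule, sensitivity analysis or dropout allowance.

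**The concern.** Two of the reasons for which a participant can be judged unsuitable to go on, harm and poor compliance, are closely tied to two of the primary outcomes, pain and compliance. Those removed are therefore likely to be people for whom the device worked badly or who did not wear it. If their outcomes are not collected, or their records fall out of the analysis, what remains is a selected group.

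The study has one arm, so there is no comparison group in which the same selection would show. Removal is a matter of judgement, and Consent Process, item 5, notes that a co-investigator is an innovator of the device, so a rule fixed in advance also protects the team's credibility. The study is meant to guide changes to the device before randomised trials, and its failures are the most useful cases for that purpose.

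Item 7 concerns withdrawal by the investigator. Such a participant has not necessarily withdrawn consent, so the missing outcomes may well be recoverable.

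**Working it through.** **1. The plan's own figure.** Study Design, item 8: "To meet a power of 0.8 and alpha of 95% with effect size of 1.35, at least 10 human subjects will be needed". The powered endpoint is daily-living function, compared between baseline and Week 4. I read the alpha as 5% two-sided; the type of effect size is not stated. With a noncentral t calculation at d = 1.35:
- Two-sample t-test: 10 per group (power 0.814; 9 per group gives 0.767). This reproduces the 10.
- Paired t-test, which fits a before-and-after contrast: 7 participants (power 0.843). At n = 10, paired power is 0.966; at n = 8 it is 0.903.

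On the paired reading, losing a few participants costs little power. The issue is bias, not power.

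**2. Inputs for the bias illustration.**
- N = 20, from Study Design, item 1 (the split between cohorts is not stated).
- Completers' mean improvement c = 1.35 SD. This is the plan's effect size for activities of daily living; the plan gives none for pain. I treat it as SD units of change.
- Number withdrawn w, and their true mean change m: **assumed**, with w from 1 to 4 and m from 0 to −1 SD. The documents give neither.

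**3. Formula.** All-subject mean = [(N − w) × c + w × m] / N. Overstatement by a completers-only mean = w × (c − m) / N.

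| w of 20 | m = 0: all-subject mean (overstatement) | m = −1: all-subject mean (overstatement) |
|---|---|---|
| 1 | 25.65/20 = 1.28 (0.07 SD) | 24.65/20 = 1.23 (0.12 SD) |
| 2 | 24.30/20 = 1.22 (0.14 SD) | 22.30/20 = 1.12 (0.24 SD) |
| 4 | 21.60/20 = 1.08 (0.27 SD) | 17.60/20 = 0.88 (0.47 SD) |

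In relative terms, 1.35/1.215 = 1.11 for two withdrawn with no change, and 1.35/0.88 = 1.53 for four withdrawn and 1 SD worse. If m = 1.35 the overstatement is 0.

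**4. Compliance, as a limiting case.** Suppose 4 of 20 are non-compliant, all four are removed, and all 16 who remain are compliant. With everyone counted: 16/20 = 80% (exact 95% CI 56–94%). With completers only: 16/16 = 100% (79–100%).

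**5. Chance that the question arises.** The probability of at least one withdrawal among 20 is 1 − (1 − p)^20. For an assumed p of 5%, 10% or 20% this is 0.64, 0.88 or 0.99.

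**The case against.** The strongest reply is that the documents are silent rather than wrong. A reader might infer that outcome collection stops at investigator withdrawal, or that the analysis is complete-case; neither is stated. Some follow-up is to be discussed, and the data cut-off in item 8 is tied to withdrawal of consent, which investigator withdrawal need not involve. This stands, and it is why the point is conditional. It does not remove the gap: no outcome assessment is named for these participants, and classical repeated measures ANOVA would leave them out.

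Other points also carry weight:
- The compliance ground sits in the eligibility list, not in the withdrawal section. Its wording about continuing does reach people already enrolled, but no passage removes non-compliers from a denominator, and no compliance denominator is defined.
- Risk and Benefits, item 2, provides a modified or new device for problems of fit or feel, and refers separately to ending the intervention. Ordinary device problems are therefore not sent straight to withdrawal.
- Device risks are listed only as infrequent, so four of 20 withdrawn and 1 SD worse is an extreme case.
- Diary cards and the 48-hour call may capture some worsening, though they do not replace the questionnaires.

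A mixed model would help. A participant with only a baseline score is not worthless in a likelihood model that treats baseline as a response. But the model assumes that those removed would have followed a course like that of similar participants who stayed, which is doubtful when harm is the reason for removal.

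**Conclusion.** The point holds as a conditional one. The plan allows removal for harm and names compliance as a reason not to continue, makes pain and compliance primary, specifies no outcome assessment at or after investigator withdrawal, and names an analysis that usually discards incomplete records. Followed as written, this single-arm study would tend to lose the device's failures, and the likely direction of bias favours the device.

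For 1 to 4 withdrawals of 20, and withdrawn participants changing by 0 to −1 SD, a completers-only mean would be too high by about 0.07 to 0.47 SD. This rests on assumed withdrawals and on an effect size stated for activities of daily living rather than pain. A reader might go further and conclude that the results are biased. The documents do not support that: withdrawal is discretionary, its frequency is unknown, and the bias vanishes if withdrawn participants fare as well as completers. The plan should still be changed, because the change is small and the lost outcomes cannot easily be recovered later.

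**What to change.** Add a few sentences to Risk and Benefits, item 8, and Study Design, item 8:

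- **Data collection.** Separate stopping the device from leaving the study. With the participant's agreement, complete the patient-reported questionnaires and the device survey at the time of withdrawal and at each remaining scheduled visit (Week 2 and Week 4; also Week 8 and Week 12 in Cohort 2).
- **Analysis set.** Analyse everyone given a device, using all available visits, for example with a likelihood mixed model. State that poor compliance is not a reason to leave anyone out of the analysis.
- **Compliance.** Report device use over the full planned period with everyone in the denominator. Show stops for harm separately from non-adherence, so that tolerability is not counted as poor adherence.
- **Sensitivity analysis.** Assign the baseline value (no improvement) to those withdrawn for device-related reasons.
- **Reporting.** Give the number of withdrawals by reason.

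Clinical decisions on withdrawal are unchanged. The cost is at most about 25 minutes of questionnaires per assessment for a few participants, plus the device survey. The 25 minutes is the plan's estimate for all five instruments, two of them investigator-rated. The estimate of benefit may also come out less favourable.
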